Cover Page

Study Protocol

Study Title: Unilateral Strength Training and Mirror Therapy for Enhancing Upper Limb Motor Function Post Stroke: A Pilot Randomised Controlled Trial

Document creation date: March 20th 2015

NCT number [not yet assigned].

Identifiers: [NCT ID not yet assigned]

Study Protocol for Unilateral Strength Training and Mirror Therapy for the Upper Limb in Chronic Stroke Patients ([name], IT Sligo, Ireland).

Assessments will take place in the Institute of Technology Sligo, in the health science physiology laboratory located in the main building on campus. The principal researcher/ research student [name] along with a second exercise professional will call to participants' homes for approximately 30 minutes per day, 3 days per week for 4 weeks to instruct and supervise the training intervention. A total of 32 participants will be randomly assigned to one of two conditions.

For the duration of the intervention participants will be seated on a standard chair in front of a standard table. They will be asked to wear a loose fitting top so that the fabric can be rolled above the elbow joint and to take off any jewellery. The participant's less-affected (LA) upper limb will be strapped into a custom made arm brace consistently holding the elbow joint at an 85° angle, the more-affected (MA) arm will rest on the table. The warm-up includes 1 minute of dynamic elbow extensions without resistance and 1 set of 5 repetitions of unilateral (LA side) isometric elbow extensions performed at perceived 50% of maximal voluntary contractions. According to maximal strength training guidelines, the main part of the training programme consists of 4 sets of 5 maximal effort isometric elbow extensions (LA limb only) held for 5 seconds with 5 seconds rest between repetitions and 3 minutes rest between sets. The principal researcher will verbally guide each participant through the intervention. Participants in the experimental group will observe the reflection of the LA training limb in a Perspex mirror placed in their mid-sagittal plane. The angle of the mirror can be adjusted according to participant preference to gain a full view of the LA limb. Prompts to focus on the reflection in the mirror will be given before each set. Participants in the control group will exercise without a mirror entirely.

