Cover Page

Statistical Analysis Plan

Study Title: Unilateral Strength Training and Mirror Therapy for Enhancing Upper Limb Motor Function Post Stroke: A Pilot Randomised Controlled Trial

Document creation date: March 20th 2015

NCT number [not yet assigned].

Identifiers: [NCT ID not yet assigned]

Statistical Analysis Plan for Unilateral Strength Training and Mirror Therapy for the Upper Limb in Chronic Stroke Patients ([name], IT Sligo, Ireland).

Data were analysed using the Statistical Package for Social Sciences (SPSS) for Windows (Version X, Chicago, IL, USA). All variables were tested for conformity to normal distribution using a combination of the visual method (histograms) and the Shapiro-Wilk test. Demographic characteristics and outcome variables are described as mean \pm SD. Possible differences between groups at baseline were analysed using the independent-t-test, Mann-Whitney U test or Chi-square test. Between group differences (ST vs MST) in change from T1 to T2 and in change from T1 to T3 were determined using the independent-sample-t-test (normal distribution) or the Mann-Whitney U test (non-normal distribution or non-continuous scale). Within group differences (T1 vs T2/ T1 vs T3) were determined using the paired-sample-t-test (normal distribution) or the Wilcoxon Signed Rank Test (non-normal distribution or non-continuous scale). P-values < 0.05 were considered to be statistically significant. Between group effect sizes, the difference in means and pooled SD was calculated using an online calculator (<https://www.uccs.edu/~lbecker/>) for parametric tests or $r=Z/\sqrt{n}$ for non-parametric tests. Within group effect size was calculated as paired differences Cohen's $d = \text{mean}/Sd$ for parametric tests or $r=Z/\sqrt{n}$ for non-parametric tests. Values for Cohen's $d = 0.2, 0.5$, and 0.8 were interpreted as small, medium, and large respectively; $0.1, 0.3$, and 0.5 were defined as small, medium and large for r .

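### Separate T1–T2 and T1–T3 change-score tests leave out anyone without T3 and ignore their T2 value; the T3 contrast is biased if loss depends on response and differs by arm, and it is less precise than a baseline-adjusted analysis in any case

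*SAP*

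**What the plan says.** The Protocol's opening section sets the size: "A total of 32 participants will be randomly assigned to one of two conditions". It gives no derivation, allocation ratio or allowance for loss. Training runs "3 days per week for 4 weeks to instruct and supervise the training intervention".

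The SAP compares arms visit by visit: group differences "in change from T1 to T2 and in change from T1 to T3 were determined using the independent-sample-t-test", "or the Mann-Whitney U test (non-normal distribution or non-continuous scale"). The within-arm tests have the same structure: "Within group differences (T1 vs T2/ T1 vs T3) were determined using the paired-sample-t-test", or the signed-rank equivalent. The significance rule is "P-values < 0.05 were considered to be statistically significant".

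Neither document defines T1, T2 or T3, names the outcomes, states an analysis set, gives an expected dropout rate, or says what is done when a visit is missing.

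**The concern.** A T1–T3 change needs both visits. With no rule for filling in a missing T3, the analyst following the SAP runs the T3 test on those who attended T3 and the T2 test on those who attended T2. The two contrasts can then describe different subsets of the 32. Anyone seen at T2 but not T3 has already shown how they responded, and the T3 test ignores it.

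If people who have done poorly by T2 are more likely to leave, and more of them leave one arm, the arm that loses more looks better at T3 than it should. With about 16 per arm, a few such losses can move the estimate. This is a pilot, so the T3 estimate may be carried into the design of a later trial.

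The second issue does not depend on dropout. A raw change score uses T1 less efficiently than adjustment for T1 as a covariate, which matters with so few participants.

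**Working it through.** **Inputs from the documents.** 32 participants, two arms, separate two-sample tests on change, significance level 0.05. The 32 cannot be reproduced, because no power, effect, SD or dropout is given.

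**Assumptions (not in the documents).** 16 per arm; two-sided tests; normal outcome with SD 1 at each visit; correlations 0.7 (T1–T2), 0.7 (T1–T3) and 0.8 (T2–T3); true T3 effect 0.5 SD in favour of the mirror arm (zero for null rejection). Loss occurs after T2, with weight exp(−kz), where z is the standardised T1–T2 change. Strong selection is k = 2: someone 1 SD poorer is e² ≈ 7 times as likely to leave. Weak selection is k = 0.5, a factor of e^0.5 ≈ 1.6.

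**1. Why selection on T2 reaches T3.** The slope of T1–T3 change on T1–T2 change is covariance over variance:

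- covariance = 0.8 − 0.7 − 0.7 + 1 = 0.4
- variance = 1 + 1 − 2(0.7) = 0.6
- slope = 0.4/0.6 = 0.67

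About two thirds of any between-arm imbalance in T2 change among those who stay therefore passes into the T3 contrast.

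**2. Size of the bias (mirror minus control, baseline SD units; simulation).**

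| Lost, control v mirror | Selection | Bias, planned T3 test | Null rejection |
|---|---|---|---|
| 0 v 0 | none | 0 | about 5% |
| 3 v 3 | random | 0 | about 5% |
| 2 v 1 | strong | −0.04 to −0.05 | not tabulated |
| 4 v 2 | weak | −0.04 | 5–6% |
| 4 v 1 | weak | −0.05 | 5–6% |
| 4 v 2 | strong | −0.08 | 6.6–6.9% |
| 4 v 1 | strong | −0.12 | 7.6–7.7% |

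A likelihood model that uses T1, T2 and T3 has bias of about 0.00 in these scenarios. That is by construction, because loss here depends only on the observed T1 and T2. If loss depends instead on the unseen T3 value, about −0.11 SD remains in the model.

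**3. Scale.**

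- Relative to the assumed effect: 0.12/0.5 = 24% at the top of the table; 0.04/0.5 = 8% to 0.05/0.5 = 10% in the milder cases.
- Relative to the complete-data standard error: 0.12/0.272 = 0.44.
- As Cohen's d on change: the SD of change is √0.6 = 0.775, so 0.12/0.775 = 0.15, which is below the 0.2 that the SAP labels small.

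**4. Precision with no dropout.**

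- Change score: √(0.6 × 2/16) = 0.274; simulated 0.272.
- Adjusted for T1: residual variance 1 − 0.7² = 0.51, so √(0.51 × 2/16) = 0.252 before the small cost of estimating the slope; simulated 0.255.
- Ratio 0.272/0.255 = 1.07.

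**5. Precision with 3 lost per arm at random.** Simulated standard errors are 0.301 (change score), 0.283 (T3 completers, adjusted for T1) and 0.275 (likelihood model).

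- Whole gap: 0.301/0.275 = 1.09.
- Baseline adjustment: 0.301/0.283 = 1.06.
- Keeping the T2 data of those lost: 0.283/0.275 = 1.03.

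**The case against.** The strongest reply is that the SAP never says people without T3 are excluded. A t-test on change can be run after imputation, so the gap is an unstated missing-data rule and not a fault of the test. It is true that exclusion is inferred. But with no imputation or joint model in the plan, leaving those people out is what the written analysis does. The proposed model is also more precise with complete data, so the point goes beyond asking for a policy to be written down.

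Several stronger readings are tempting and are not supported:

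- **That the T3 result will be biased.** No dropout figure exists. The larger values need both unequal loss and strong selection. Under weak selection, or with 2 versus 1 lost, the bias is a tenth of the assumed effect or less.
- **That unequal loss is likely because controls have no mirror.** The Protocol describes the same supervised home sessions for both arms. Unequal loss is possible, but the documents do not show it to be likely.
- **That the T3 test is safe if loss is balanced, or unrelated to T2 response.** Neither condition is enough. Equal counts can hide different reasons for leaving, and loss can depend on T3 itself.
- **That the 9% gap in standard error is the price of dropout.** Most of it is baseline adjustment; about 3% comes from retaining T2 data.
- **That T3 is the retention result.** Neither document defines T3 in that way.
- **That a mixed model cures the problem.** It does so only when loss depends on observed data.

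It is also fair to say that the outcomes are unnamed, so how many would suit such a model is unknown.

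**Conclusion.** The point holds as a conditional one. As written, the T3 comparison uses only those with T3 and ignores the T2 data of the rest. It is biased if loss depends on T2 response and differs between arms. Under the stated assumptions the bias runs from 0 to about −0.12 SD, with null rejection rising from 5% to about 7.7%; the upper end needs 4 versus 1 lost and strong selection. The direction follows from assuming that the control arm loses more, and would reverse if the mirror arm did. Other correlations, or loss confined to one arm, would give other values.

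The loss of precision from using an unadjusted change score is about 7% and does not depend on dropout, though it does depend on the assumed correlation of 0.7. Together these justify changing the between-group analysis of continuous outcomes. They do not show that the planned T3 result is wrong.

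**What to change.** For each continuous outcome, replace the two between-group change-score t-tests with one repeated-measures mixed model:

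- outcomes T2 and T3;
- terms for T1, T1 × time, group, time and group × time;
- unstructured covariance for the two visits and small-sample degrees of freedom (for example Kenward-Roger);
- all randomised participants in their assigned arm;
- the group difference reported at T2 and at T3 with its interval.

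Someone with neither T2 nor T3 adds nothing to this model and must be covered by the reporting and sensitivity analysis below.

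Keep a between-group rank or ordinal analysis for ordinal outcomes. Report the number of missing visits and the reasons by arm and visit. Add a missing-not-at-random sensitivity analysis for continuous as well as ordinal outcomes, for example shifting the missing T3 values by a range of amounts in each arm, or best-case and worst-case values on an ordinal scale. Define T1, T2 and T3 in the SAP.

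The cost is about a paragraph of SAP text, slightly more analysis work, and one or two extra parameters to estimate. No new data or participants are needed. With complete data the T3 estimate equals that of a baseline-adjusted ANCOVA.

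### Do the within-arm paired tests, run under the same P<0.05 rule as the randomised comparison, put the conclusion about the mirror at risk?

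*SAP*

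**What the plan says.** The Statistical Analysis Plan is one unnumbered section. It sets out the randomised comparison first, as "Between group differences (ST vs MST) in change from T1 to T2 and in change from T1 to T3", tested by an independent t-test or a Mann-Whitney U test. It then adds the within-arm tests: "Within group differences (T1 vs T2/ T1 vs T3) were determined using the paired-sample-t-test", "or the Wilcoxon Signed Rank Test (non-normal distribution or non-continuous scale").

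A single threshold follows, not limited to either kind of test: "P-values < 0.05 were considered to be statistically significant". Effect sizes are defined separately for the two purposes. The between-group one uses the difference in means and a pooled SD. For the other, "Within group effect size was calculated as paired differences", that is, mean over SD. One set of size labels then serves both (for d of 0.2, 0.5 "and 0.8 were interpreted as small, medium, and large respectively").

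The Protocol states the design: "A total of 32 participants will be randomly assigned to one of two conditions". It describes one training programme. What separates the arms is the mirror, with prompts to look at it: "Participants in the experimental group will observe the reflection of the LA training limb in a Perspex mirror", while controls train without one. The SAP does not call the within-arm tests descriptive, and it does not say which test carries the conclusion about the mirror.

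**The concern.** Randomisation protects only the comparison between arms. A change inside one arm mixes training with time, retest learning, regression to the mean and attention. With no untrained arm, the design cannot separate these, and since both arms train alike, a within-arm change says nothing specific about the mirror.

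The SAP nevertheless lets each within-arm change be called significant and graded for size, on the same footing as the randomised test. The familiar error is to find P<0.05 in the mirror arm, P>0.05 in the control arm, and conclude that the mirror worked. That inference is wrong, and in a small trial the pattern can arise often when the arms truly change by the same amount. If the report relied on it, the trial's main message could be false.

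**Working it through.** The documents contain no effect size, SD, power or sample-size calculation, so there is no stated figure to reproduce. The check is how often the misleading pattern would occur, and what the planned randomised test would show when it does.

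**Inputs**
- Total of 32 in two arms (Protocol). The ratio is not stated; 16 per arm assumed.
- Threshold 0.05 (SAP). Two-sided assumed.
- MST taken as the mirror arm; the SAP does not spell this out.
- Normal changes, with the same true mean change and SD in both arms, so no mirror effect. One outcome, one time point.
- d_z, the true mean change divided by the SD of change, is not given, so a range is shown.

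**Step 1: power of one paired t-test.** Two-sided 0.05, 15 degrees of freedom, noncentrality d_z × √16 = 4 d_z. At d_z = 0.5 the noncentrality is 2.0 and the power is p = 0.465.

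**Step 2: significant in the mirror arm only.** The arms are independent, so the probability is p(1 − p). At d_z = 0.5 this is 0.465 × 0.535 = 0.249.

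| d_z | p | p(1 − p) | Simulated, Wilcoxon branch (large-sample p-value) |
|---|---|---|---|
| 0 | 0.050 | 4.8% | 4.8% |
| 0.2 | 0.117 | 10.3% | 10.2% |
| 0.5 | 0.465 | 24.9% | 24.8% |
| 0.8 | 0.848 | 12.9% | 13.6% |
| 1.0 | 0.962 | 3.7% | 4.2% |
| 1.1 | 0.984 | 1.6% | 1.9% |
| 1.2 | 0.994 | 0.6% | 0.8% |

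The function p(1 − p) cannot exceed 0.5 × 0.5 = 25%. That ceiling applies to any two-arm trial with equal within-arm power; it is not a property of this plan. At d_z = 0 the 4.8% also counts significant worsening. By symmetry, improvement alone is about half of it, 4.75/2 ≈ 2.4%.

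**Step 3: the planned between-group test under the same conditions.** Simulated rejection rates are about 5.0% (t-test) and 4.7% (Mann-Whitney) across the whole range of d_z, because a change common to both arms cancels.

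**Step 4: the two results side by side.** In simulation at d_z = 0.5, 24.8% of trials showed the mirror-arm-only pattern, and about 2.3% of all trials showed it together with a significant between-group test. Hence 1 − 2.3/24.8 ≈ 91% of the trials with the misleading pattern also carry a non-significant randomised comparison. At any d_z, the share of all trials showing both cannot exceed the 5% rejection rate of the between-group test.

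**Step 5: what the text does with the paired tests.** The SAP says they determine within-group differences, which they do validly. No sentence compares their p-values between arms or attributes a within-arm change to the mirror or to training.

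**The case for a change.** The strongest case for a change is that a SAP exists to fix in advance which result answers the question, and this one does not say so. The sample makes the temptation real. At 16 per arm, 80% power needs a d_z of 0.75 within an arm but a d of 1.02 between arms, and between-group power at d = 0.5 is only 28%. A non-significant randomised result beside significant within-arm changes is therefore a likely outcome. Exactly one arm being significant, in either direction, reaches 2 × 0.465 × 0.535 ≈ 50% at d_z = 0.5. Pilot status, if anything, argues for less significance testing.

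The facts in this stand; the step from them to a defect does not. Low between-group power is a consequence of the sample size and is unaltered by dropping or relabelling the paired tests. The misreading requires someone to set aside a planned comparison reported for the same outcome. Removing P<0.05 from valid within-arm tests would change no between-group result, and whether a pilot reports within-arm p-values is largely a matter of preference.

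The shared size labels do not add to the case. The two effect sizes are defined separately, so a reader can tell which is meant, and no wrong conclusion about the mirror has been shown to follow from the common labels.

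**Conclusion.** No change to the plan follows. This is a gap in interpretation that analysts fill sensibly: the SAP contains the correct randomised test of change, the paired tests are valid for their own narrower question, and the plan proposes no cross-arm reading of them. Followed as written, it tests the mirror effect with a false-positive rate of about 5% per outcome and time point.

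The 0.6% to 25% range is the frequency of a pattern open to misreading, not an error rate of the plan. It rests on 16 per arm, two-sided tests, normal changes with equal SDs, and an assumed d_z. With 18 in the mirror arm and 14 in the control arm, the d_z = 0.5 figure is about 30%; with the split reversed it is about 20%. The caution belongs to whoever writes or reads the report: only the ST against MST comparison bears on the mirror, and a within-arm change should carry no causal reading.
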